6.2 Definitions of serious adverse event

A serious adverse event (SAE) is an AE occurring during any study phase (ie, run-in, treatment, washout, follow-up), that fulfils one or more of the following criteria:

- Results in death
- Is immediately life-threatening
- Requires in-patient hospitalisation or prolongation of existing hospitalisation
- Results in persistent or significant disability/incapacity or substantial disruption of the ability to conduct normal life functions
- Is a congenital abnormality or birth defect
- Is an important medical event that may jeopardise the subject or may require medical intervention to prevent one of the outcomes listed above.

For further guidance on the definition of a SAE, see [Appendix A](#) to the Clinical Study Protocol.

6.3 Recording of adverse events

6.3.1 Time period for collection of adverse events

Adverse Events will be collected from time of signature of informed consent throughout the treatment period and including the safety follow-up period. The follow-up period is defined as 28 days after study treatment is discontinued. SAEs occurring in the follow-up period should be reported to AstraZeneca in the usual manner (see Section 6.4).

Following discontinuation of AZD9291, SAEs considered related to study procedures should continue to be collected as outlined in [Table 6](#)

After the final DCO, there may be some patients remaining on study treatment. For these patients who are continuing to receive AZD9291 AstraZeneca will collect information (during the treatment period and for 30 days safety follow up after last dose) on SAEs, deaths (including those due to disease progression), pregnancy, overdose, discontinuation due to AEs/SAEs and drug accountability only.

Table 6 Summary of recording and follow-up of adverse events and deaths

	Consent to Treatment Period	Until 28-day Follow-up Visit (safety follow-up period)	Post 28-day Follow-up visit but prior to progression (if applicable)	Post 28-day Follow-up visit and post progression (survival follow-up period)
Collect all new AEs in CRF	Yes	Yes	No	No
Collect all ongoing AEs in CRF	Yes	Yes	Yes	Yes
Collect all study procedure-related SAEs in CRF	Yes	Yes	Yes	Yes
Death due to AE, or unknown cause ^a	Yes	Yes	No	No

^a For example, death not due to disease progression, refer to Section 6.3.10

6.3.2 Follow-up of unresolved adverse events

Any AEs that are unresolved are followed up by the investigator for as long as medically indicated. AstraZeneca retains the right to request additional information for any patient with ongoing AE(s) /SAE(s) at the end of the study, if judged necessary.

If an investigator learns of any SAEs, including death, at any time and he/she considers there is a reasonable possibility that the event is related to AZD9291, the investigator should notify AstraZeneca.

6.3.3 Variables

The following variables will be collected for each AE:

- AE (verbatim)
- The date when the AE started and stopped
- Changes in CTCAE grade (for skin reactions and diarrhoea only); maximum CTCAE grade for all other AEs
- Whether the AE is serious or not
- Investigator causality rating against the Investigational Product (yes or no)
- Action taken with regard to investigational product
- Outcome

In addition, the following variables will be collected for SAEs:

- Date AE met criteria for SAE
- Date Investigator became aware of SAE
- AE is serious due to
- Date of hospitalisation
- Date of discharge
- Causality assessment in relation to Study procedure(s)
- Causality assessment in relation to other medication
- Description of AE

It is important to distinguish between serious and severe AEs. Severity is a measure of intensity whereas seriousness is defined by the criteria in Section 6.2. An AE of severe intensity need not necessarily be considered serious. For example, rash that covers >30% of the body may be considered severe but not a SAE unless it meets the criteria shown in Section 6.2. On the other hand, a stroke that results in only a limited degree of disability may be considered a mild stroke but would be a SAE when it satisfies the criteria shown in Section 6.2.

The grading scales found in the current National Cancer Institute CTCAE version 4 will be utilised for all events with an assigned CTCAE grading. For those events without assigned CTCAE grades, the recommendation in the CTCAE criteria that converts mild, moderate and severe events into CTCAE grades should be used. A copy of the current CTCAE version can be downloaded from the Cancer Therapy Evaluation Program website (<http://ctep.cancer.gov>).

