8.5 Calculation or derivation of safety variable(s)

Adverse events

Adverse Events (both in terms of MedDRA preferred terms and CTCAE grade) will be listed individually by patient.

Any AE occurring before treatment with AZD9291 will be included in the data listings but will not be included in the summary tables of AEs.

Any AE occurring within 28 days of discontinuation of investigational product (ie, the last dose of AZD9291) will be included in the AE summaries. Any events in this period that occur after a patient has received further therapy for cancer (following discontinuation of AZD9291) will be flagged in the data listings.

A separate data listing of AEs occurring more than 28 days after discontinuation of AZD9291 will be produced. These events will not be included in AE summaries

Other significant adverse events (OAEs)

During the evaluation of the AE data, an AstraZeneca medically qualified expert will review the list of AEs that were not reported as SAEs and AEs leading to discontinuation. Based on the expert's judgement, significant AEs of particular clinical importance may, after consultation with the Global Patient Safety Physician, be considered OAEs and reported as such in the CSR. A similar review of laboratory/vital signs/ECG data will be performed for identification of OAEs.

Examples of these could be marked haematological and other laboratory abnormalities, and certain events that lead to intervention (other than those already classified as serious), dose reduction or significant additional treatment.

Safety Assessments

For change from baseline summaries for vital signs, laboratory data, LVEF, ECGs and physical examination, the baseline value will be the latest result obtained prior to the start of investigational product.

The denominator used in laboratory summaries will only include evaluable patients, in other words those who had sufficient data to have the possibility of an abnormality.

For example:

- If a CTCAE criterion involves a change from baseline, evaluable patients would have both a pre-dose and at least 1 post-dose value recorded
- If a CTCAE criterion does not consider changes from baseline, to be evaluable the patient need only have 1 post dose-value recorded

The denominator in vital signs data should include only those patients with recorded data.

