AEs (both in terms of MedDRA preferred terms and CTCAE grade) will be listed individually by patient. The number of patients experiencing each AE will be summarised by CTCAE grade.

Other safety data will be assessed in terms of physical examination, clinical chemistry, haematology, vital signs and LVEFs.

Exposure to AZD9291 will be summarised. Time on study and AZD9291 dose reductions and dose delays will also be summarised.

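### For most adverse events only an undated maximum grade is recorded, so worsening after the 28-day window can enter the on-treatment severity tables

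*Protocol*

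**What the plan says.** Section 6.3.3 lists what is recorded for each AE. For timing it is "The date when the AE started and stopped". For severity it is "Changes in CTCAE grade (for skin reactions and diarrhoea only); maximum CTCAE grade for all other AEs". No date is requested for the maximum. Sections 6.7.1 and 6.7.2 repeat that grade changes are captured for skin reactions and diarrhoea.

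Table 6 in section 6.3.1 sets the collection periods. The row "Collect all new AEs in CRF" reads Yes up to the 28-day visit and No in both later periods. The row "Collect all ongoing AEs in CRF" reads Yes in all four periods, including survival follow-up. Section 6.3.2 adds: "Any AEs that are unresolved are followed up by the investigator for as long as medically indicated".

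On the analysis side, section 8.5 says: "Any AE occurring within 28 days of discontinuation of investigational product (ie, the last dose of AZD9291) will be included in the AE summaries". AEs that occur later are listed separately and left out of the summaries. Section 8.7.2 then says: "The number of patients experiencing each AE will be summarised by CTCAE grade".

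**The concern.** Each rule is reasonable alone. Together they apply one time limit to the event and no time limit to its grade. An AE enters the table because it arose on treatment or within 28 days of the last dose. The grade it is counted under is the worst one ever entered on a record that may stay open long afterwards.

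Safety is a secondary objective of a single-arm study, so the grade distribution is read directly as the tolerability of AZD9291, with no control arm to show a shared bias. Section 1.1 describes platinum-based doublet chemotherapy as a treatment after EGFR-TKI failure, and its listed toxicities include nausea, vomiting, fatigue and peripheral neuropathy. Section 4.3.4 expects later anti-cancer therapy and records it. An AE left open from AZD9291 could plausibly worsen on such treatment.

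**Working it through.** The plan states no figure for this point, so there is none to reproduce. The check is to follow one event through the rules and look for anything that stops it.

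**Traced example.** Fatigue starts at grade 1 on AZD9291 and is unresolved at the 28-day visit. The patient then starts another therapy and the fatigue reaches grade 3.

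1. *Can it be entered as a new AE?* No. Table 6 has stopped collecting new AEs in the CRF. The exception is procedure-related SAEs, and section 6.3.2 separately asks for notification of SAEs judged related to AZD9291.
2. *Is the existing record still open?* Yes, by the ongoing-AE row of Table 6.
3. *Which field can hold the worsening?* Only the maximum grade, which would become 3 without a date.
4. *Does the AE enter the summaries?* Yes. It occurred on treatment, so section 8.5 includes it.
5. *At which grade?* Grade 3, because the maximum is the only grade held.

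**Safeguards examined.**

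- Section 8.5 flags events that arise after further cancer therapy. This works on when the event occurs, covers only the 28-day window and affects listings only. The traced event did not begin after further therapy.
- The separate listing of AEs beyond 28 days also works on when the event occurs.
- Causality to the investigational product is a single yes/no per AE (sections 6.3.3 and 6.3.4). Causality to other medication is collected only for SAEs. A related grade 1 event could therefore become a related grade 3 event.
- AE start and stop dates, set against anti-cancer therapy records (section 4.3.4), can show which AEs overlap a later therapy. They cannot show the grade held before it.
- An analysis plan can restrict a table to on-treatment grades only if those grades are dated or were recorded at the cut. For most AEs neither holds.

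**Scale.** The protocol gives neither the number of AEs left open nor the number that worsen. It does fix what one affected patient is worth:

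- all patients: 1/175 = 0.6 percentage points;
- TKI-only cohort, 50 + 8 = 58 planned: 1/58 = 1.7 points;
- TKI-plus-platinum cohort, 100 + 17 = 117 planned: 1/117 = 0.9 points.

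For the rate of patients with any grade 3 or higher AE, a patient who already had such an event on treatment adds nothing. For a single AE term, each patient whose grade for that term rises counts in full.

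**The case against.** The strongest reply is that no sentence tells sites to raise a grade after later therapy begins. Collecting an ongoing AE could mean following it to its stop date and outcome. The AE definition in section 6.1 includes deterioration of an existing condition, so worsening on a new regimen might count as a new AE. After the 28-day visit it would then not be recorded at all. Practical occasion is also limited. Survival follow-up (section 4.3.4) may be a telephone call and does not list AE grading, and the Table 1 footnote on AEs after discontinuation mentions only procedure-related SAEs. All this stands as a limit on how often the problem occurs. It does not remove the problem, because nothing tells sites to stop updating the maximum, and Table 6 keeps the record open.

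Several stronger readings are tempting but not supported:

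- *Cytopenias and liver enzymes are prime examples.* Section 6.3.6 mostly excludes these. Deterioration in mandated laboratory tests is reported as an AE only if it meets an SAE criterion or causes discontinuation of the investigational product.
- *Later worsening is wholly invisible.* For SAEs the protocol collects the date of meeting SAE criteria, hospitalisation dates and causality to other medication, so serious worsening is partly dated. The database audit trail (section 9.4) would show when a field was edited, but that is the date of entry, not of worsening, and it is not an analysis variable.
- *Skin reactions and diarrhoea are already protected.* Their grade changes are collected, but neither section 8.5 nor 8.7.2 says that the summaries stop at day 28.

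It can also be said that the choice of grade for a table belongs in the SAP. For skin reactions and diarrhoea that is fair. For all other AEs the SAP cannot supply a grade that was not captured.

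**Conclusion.** The point holds as a mismatch between data capture and the analysis window. For AEs other than skin reactions and diarrhoea, the tabulated grade can come from after the 28-day window that decides whether the event is tabulated. The AE variables collected cannot restore the earlier grade.

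The conclusion rests on three conditions: the AE is still open at the end of the window, it later worsens, and the site updates the maximum. The third is an inference from Table 6 and the word maximum, not an explicit instruction. The main exposure is non-serious, non-laboratory AEs.

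The bias is upward only, because a maximum cannot fall. It affects descriptive, all-causality safety tables and does not touch the response-rate endpoint. A reader might infer that grade 3 or higher rates are inflated by a known number of points. The protocol gives no frequencies from which to derive one, and any such figure would rest on invented inputs. The matter still deserves correction, because the protocol already fixes a 28-day window for events and only needs to apply it to severity.

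**What to change.** In section 6.3.3, define the value recorded for AEs other than skin reactions and diarrhoea as the maximum CTCAE grade reached up to 28 days after the last dose of AZD9291. Alternatively, keep the maximum as it is and require dated grade changes for AEs still open at the 28-day visit.

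In section 8.5, state that summaries by grade use the highest grade reached from first dose to 28 days after last dose. Say that this includes skin reactions and diarrhoea, and that later worsening is listed only.

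This limit would still admit worsening on a new therapy started within the 28 days. That matches section 8.5, which keeps events in that period in the summaries and flags them in listings.

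The cost is one sentence in each section, a short addition to CRF completion guidance and, under the alternative, a little extra data entry for AEs still open at the visit. No treatment rule or follow-up obligation changes.

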6.3.4 Causality collection

The Investigator will assess causal relationship between Investigational Product and each Adverse Event, and answer 'yes' or 'no' to the question 'Do you consider that there is a reasonable possibility that the event may have been caused by the investigational product?'

For SAEs causal relationship will also be assessed for other medication and study procedures. Note that for SAEs that could be associated with any study procedure the causal relationship is implied as 'yes'.

A guide to the interpretation of the causality question is found in [Appendix A](#) to the Clinical Study Protocol.

6.3.5 Adverse events based on signs and symptoms

All AEs spontaneously reported by the subject or care provider or reported in response to the open question from the study personnel: 'Have you had any health problems since the previous visit/you were last asked?', or revealed by observation will be collected and recorded

in the CRF. When collecting AEs, the recording of diagnoses is preferred (when possible) to recording a list of signs and symptoms. However, if a diagnosis is known and there are other signs or symptoms that are not generally part of the diagnosis, the diagnosis and each sign or symptom will be recorded separately.

6.3.6 Adverse events based on examinations and tests

The results from protocol mandated laboratory tests and vital signs will be summarised in the clinical study report. Deterioration as compared to baseline in protocol-mandated parameters should therefore only be reported as AEs if they fulfil any of the SAE criteria or are the reason for discontinuation of treatment with the investigational product unless clearly due to progression of disease under study (see Section 6.3.8).

If deterioration in a laboratory value, vital sign, ECG, or other safety assessment is associated with clinical signs and symptoms, the sign or symptom will be reported as an AE and the associated laboratory result or other finding will be considered as additional information. Wherever possible the reporting Investigator uses the clinical, rather than the laboratory term (eg, anaemia versus low haemoglobin value). In the absence of clinical signs or symptoms, clinically relevant deteriorations in non-mandated parameters should be reported as AE(s).

Deterioration of a laboratory value, which is unequivocally due to disease progression, should not be reported as an AE/SAE.

Any new or aggravated clinically relevant abnormal medical finding at a physical examination as compared with the baseline assessment will be reported as an AE.

6.3.7 Hy's law

Cases where a subject shows an AST or ALT $\geq 3x$ ULN and total bilirubin $\geq 2x$ ULN may need to be reported as SAEs. Prompt reporting of cases meeting Hy's law criteria (via the SAE expedited reporting system) is required for compliance with regulatory guidelines. The investigator is responsible for, without delay, determining whether a patient meets potential Hy's law (PHL) criteria.

Details of identification of PHL cases and actions to take are detailed in [Appendix D](#).

6.3.8 Disease progression

Disease progression can be considered as a worsening of a subject's condition attributable to the disease for which the investigational product is being studied. It may be an increase in the severity of the disease under study and/or increases in the symptoms of the disease. The development of new, or progression of existing metastasis to the primary cancer under study should be considered as disease progression and not an AE. Events, which are unequivocally due to disease progression, should not be reported as an AE during the study.

6.3.9 New cancers

The development of a new cancer should be regarded as an AE and will generally meet at least one of the serious criteria. New cancers are those that are not the primary reason for the administration of the study treatment and have been identified after the patient's inclusion in this study. They do not include metastases of the original cancer.

Progression of the malignancy under study, including signs and symptoms progression, should not be reported as a serious adverse event. Hospitalization due to signs and symptoms of disease progression should not be reported as serious adverse event.

6.3.10 Handling of deaths

All deaths that occur during the study, or within the follow-up period after the administration of the last dose of investigational product, should be reported as follows:

- Death, which is unequivocally due to disease progression, should be communicated to the study monitor at the next monitoring visit and should be documented in the CRF module, but should not be reported as a SAE during the study
- Where death is not clearly due to disease progression of the disease under study the AE causing the death should be reported to the study monitor as an SAE within 24 hours. The report should contain a comment regarding the co-involvement of progression of disease, if appropriate, and should assign a single primary cause of death together with any contributory causes
- Deaths with an unknown cause should always be reported as a SAE but every effort should be made to establish a cause of death. A post-mortem may be helpful in the assessment of the cause of death, and if performed a copy of the post-mortem results (with translation of important parts into English) should be reported in an expedited fashion to an AstraZeneca representative within the usual timeframes

6.4 Reporting of serious adverse events

All SAEs have to be reported, whether or not considered causally related to the investigational product, or to the study procedure(s). All SAEs will be recorded in the CRF.

Note at the time of study completion (i.e. after final OS DCO date), the WBDC system will be decommissioned and SAE data will be collected via paper and emailed (preferably) or faxed directly to TCS (also known as AZ DES), which will be responsible for processing all SAEs onto the AZ global safety database. Drug accountability information will be stored in the patient notes at site.

If any SAE occurs in the course of the study, then Investigators or other site personnel inform the appropriate AstraZeneca representatives within one day ie, immediately but **no later than 24 hours** of when he or she becomes aware of it.

The designated AstraZeneca representative works with the Investigator to ensure that all the necessary information is provided to the AstraZeneca Patient Safety data entry site **within 1 calendar day** of initial receipt for fatal and life threatening events **and within 5 calendar days** of initial receipt for all other SAEs.

For fatal or life-threatening adverse events where important or relevant information is missing, active follow-up is undertaken immediately. Investigators or other site personnel inform AstraZeneca representatives of any follow-up information on a previously reported SAE within one calendar day ie, immediately but **no later than 24 hours** of when he or she becomes aware of it.

Once the investigators or other site personnel indicate an AE is serious in the WBDC system, an automated email alert is sent to the designated AstraZeneca representative.

If the WBDC system is not available, then the investigator or other study site personnel reports a SAE to the appropriate AstraZeneca representative by telephone.

The AstraZeneca representative will advise the investigator/study site personnel how to proceed.

The reference document for definition of expectedness is the IB for the AstraZeneca drug AZD9291 and the EU Summary of Product Characteristics (SPC) for the active comparator product (including any AstraZeneca comparator).

6.5 Overdose

Investigators are advised that any patient who receives a higher dose than intended should be monitored closely, managed with appropriate supportive care and followed up expectantly.

Such overdoses should be recorded as follows:

- An overdose with associated AEs/SAEs is recorded as the AE diagnosis/symptoms on the relevant AE/SAE modules in the CRF and on the Overdose CRF module.
- An overdose without associated symptoms is only reported on the Overdose CRF module.

If an overdose on an AstraZeneca study drug occurs in the course of the study(including the continued access), then the Investigator or other site personnel inform appropriate AstraZeneca representatives immediately, **or no later than 24 hours of when** he or she becomes aware of it.

The designated AstraZeneca representative works with the Investigator to ensure that all relevant information is provided to the AstraZeneca Patient Safety data entry site.

For overdoses associated with a SAE, the standard reporting timelines apply, see Section 6.4. For other overdoses, reporting must occur within 30 days.

For replacement of a missing dose, please refer to section 7.2.

